5.6 Definitions of Evaluability

All patients who receive any study treatment are evaluable for toxicity. Patients are evaluated from first receiving study treatment until a 30-day follow up after the conclusion of treatment or death.

All patients are evaluable for disease response unless they discontinue treatment prior to completion of Cycle 1 and have not had any disease assessment.

5.7 Concomitant Therapy and Supportive Care Guidelines

General supportive care measures, including blood and platelet transfusions, antiemetics, administration of granulocyte colony-stimulating growth factors, corticosteroids, and use of antibiotics and antivirals are permitted at the discretion of the treating physician.

It is recommended that nausea, vomiting, diarrhea, or blood pressure elevation be medically managed according to the investigator's discretion.

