	
 3. Evaluate anemia response to fostamatinib 4. Evaluate the impact of fostamatinib on transfusion requirements 5. Evaluate the impact of fostamatinib on MF symptoms 6. Evaluate the ability of fostamatinib treatment to enable initiation with ruxolitinib 7. Evaluate the impact of fostamatinib on marrow fibrosis 
Part B:
 
Primary Objective: Evaluate the safety and tolerability of fostamatinib plus ruxolitinib in patients with MF and thrombocytopenia
 
Secondary Objectives:
 
 1. Evaluate spleen response with the combination of fostamatinib and ruxolitinib 2. Evaluate the impact of fostamatinib and ruxolitinib on symptoms 3. Evaluate the ability of fostamatinib to enable sustained treatment with ruxolitinib 4. Evaluate the impact of fostamatinib and ruxolitinib on marrow fibrosis
Endpoints:	
Part A:
 
Primary Endpoint: Platelet response as defined as an increase in platelet count $\geq 50K/\text{microL}$ with at least one more confirmatory platelet count separated by at least 2 weeks (in the absence of platelet transfusion) within the first 12 weeks of fostamatinib treatment
 
Secondary Endpoints:
 
 1. Platelet response by week 12 and at end of fostamatinib monotherapy treatment 2. Number of patients eligible to initiate therapy with ruxolitinib 3. Adverse events (AEs), serious AEs (SAEs), and laboratory abnormalities on fostamatinib treatment 4. Patients who permanently discontinued fostamatinib due to fostamatinib related AEs 5. Patients who required treatment interruption of fostamatinib due to AEs 6. Patients who were dose escalated who tolerated fostamatinib dose greater than 100 mg BID 7. Patients who achieve 35% or greater reduction in spleen volume as determined by ultrasound at week 12 of fostamatinib treatment and end of fostamatinib monotherapy treatment

	
 8. Mean reduction in spleen volume as determined by ultrasound at week 12 of fostamatinib treatment and end of fostamatinib monotherapy treatment 9. Patients with 50% or greater improvement in Total Symptom Score at week 12 of treatment and end of fostamatinib monotherapy treatment 10. Patients who achieve platelet transfusion independence 11. Patients with anemia who achieve RBC transfusion independence 12. Change in marrow fibrosis by WHO grading

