5.8 Prohibited Concurrent Therapy

Patients should not receive treatment with any potent CYP3A4 inhibitors for one week prior to the start of and for the duration of study treatment.

Other chemotherapeutic or investigational agents are not permitted while the patient is receiving active treatment on protocol.

The use of thrombopoietin (TPO) stimulating agents are not permitted while the patient is receiving active treatment on protocol.

Patients cannot receive radiotherapy within 14 days prior to study enrollment or while on study.

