10.2 Hematologic Response

10.2.1 Anemia Response

Anemia response is only applicable for patients with a baseline hemoglobin level less than 10 g/dL for 8 weeks or more, and requires:

- ≥ 2 g/dL increase in hemoglobin level
OR
- becoming transfusion-independent (no RBC transfusions in past 1 month)

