10.2.2 Platelet Response

Platelet response is only applicable for patients with a baseline platelet count of less than $50 \times 10^9/L$ for 8 weeks or more, and requires:

- An absolute platelet count of at least $50 \times 10^9/L$ on two separate measurements at least 2 weeks apart

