10.3 Symptoms Response

$A \geq 50\%$ reduction in the myeloproliferative neoplasm symptom assessment total symptom score (see Appendix F)

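### Platelet counts taken after a corticosteroid is started or increased score as fostamatinib response, and no planned analysis separates them

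*Combined protocol and SAP*

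**What the plan says.** Section 5.7 begins its list of allowed measures with "General supportive care measures, including blood and platelet transfusions, antiemetics, administration of granulocyte colony-stimulating growth factors, corticosteroids" and leaves their use to the physician: "corticosteroids, and use of antibiotics and antivirals are permitted at the discretion of the treating physician". It sets no limit on dose, timing, indication or stability, and the eligibility criteria in Section 3 contain no steroid rule.

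Two other sources of a platelet rise are dealt with. The synopsis requires the Part A primary endpoint to be met "in the absence of platelet transfusion". Section 5.8 states: "The use of thrombopoietin (TPO) stimulating agents are not permitted while the patient is receiving active treatment on protocol". Section 5.8 also bars potent CYP3A4 inhibitors, other chemotherapeutic or investigational agents, and radiotherapy. It does not mention corticosteroids.

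Section 10.2.2 defines platelet response as an absolute count of at least 50 × 10⁹/L "on two separate measurements at least 2 weeks apart", and Section 12.2 uses the same definition. Neither attaches a condition on other drugs. The same holds for two secondary endpoints: anemia response in Section 10.2.1 (a hemoglobin rise, or "becoming transfusion-independent (no RBC transfusions in past 1 month") and symptom response in Section 10.3 (a 50% or greater "reduction in the myeloproliferative neoplasm symptom assessment total symptom score").

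Section 5.6 keeps patients evaluable whatever co-medication they receive. Section 12.3 plans descriptive analysis with exact 95% intervals. The Schedule of Activities has concomitant medication reviewed at screening and on Day 1 of each cycle. Section 9 lists a Transfusion Form but no concomitant-medication form.

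**The concern.** Part A asks whether fostamatinib affects platelet counts. Only one treatment is studied, so nothing in the design distinguishes a rise due to fostamatinib from a rise due to something else given at the same time. The plan accepts that logic for transfusions, which it screens out of the endpoint, and it bars thrombopoietin agents. Corticosteroids are expressly allowed, and the scoring rule has no provision for them. A patient who starts or increases a steroid in week 6 and then has two qualifying counts is a fostamatinib responder under the written definition.

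At stake is the reading of the primary response rate. The secondary count of patients able to start ruxolitinib has the same exposure. Anemia and symptom response also count as clinical improvement in Section 10.1, so the issue reaches the overall response rate that Section 12.3 will report. Because the listed case report forms do not capture steroid dates, the trial dataset may not allow the affected patients to be identified later.

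**Working it through.** **Inputs.** N = 12, one arm (Sections 12.2 and 12.4). Response means two counts of at least 50K, at least two weeks apart (Section 10.2.2). Section 12.3 specifies exact 95% intervals, taken here as Clopper-Pearson. The documents give no rate of steroid use and no steroid effect on platelets in myelofibrosis.

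**Step 1: the plan's own figures.** Section 12.4 gives two binomial probabilities for platelet response.
- At most 1 response at a true rate of 20%: 0.8¹² + 12 × 0.2 × 0.8¹¹ = 0.275. The plan states 27%.
- At least 2 responses at a true rate of 40%: 1 − 0.6¹² − 12 × 0.4 × 0.6¹¹ = 0.980. The plan states 98%.

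Both reproduce. No stated figure is in dispute, and N is unaffected.

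**Step 2: what one patient is worth.** 1/12 = 8.3 percentage points.

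| Responders | Rate | Exact 95% CI |
|---|---|---|
| 1/12 | 8.3% | 0.2% to 38.5% |
| 2/12 | 16.7% | 2.1% to 48.4% |
| 3/12 | 25.0% | 5.5% to 57.2% |
| 4/12 | 33.3% | 9.9% to 65.1% |

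Section 12.4 illustrates efficacy by contrasting at most 1 response with at least 2. A single patient moves the result from one side to the other, although the plan does not make this a decision rule.

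**Step 3: can the size of the bias be estimated?** Suppose a true rate p = 5%, a share s of patients who start a steroid, and a probability q that a starter who would not otherwise respond then meets the criterion. All three are assumptions. The apparent rate is p + (1 − p) × s × q.
- Without steroids, P(at least 2 of 12) = 11.8%.
- s = 1/12, q = 0.25: 0.05 + 0.95 × 0.083 × 0.25 = 7.0%, and P(at least 2) = 20.2%.
- s = 4/12, q = 1: 0.05 + 0.95 × 0.333 = 36.7%, and P(at least 2) = 96.7%.

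A span from 20.2% to 96.7% shows that the assumed inputs determine the answer. It is not evidence of a bias of any particular size.

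**Step 4: do other provisions close the gap?**
- Exclusion 10 bars strong CYP3A inhibitors and CYP3A inducers on study. It names no corticosteroid and so does not override the permission in Section 5.7.
- The two-week gap between counts limits the scope for a brief course to score. It does not address a longer course.
- The Day 1 medication review collects information, but no text connects it to response scoring.

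**The case against.** The strongest reply is that the causal premise is missing from the documents. Nothing in them says that corticosteroids raise platelets, hemoglobin or symptom scores in myelofibrosis. Sections 1.3 and 1.5 point to disordered blood formation and hypersplenism as causes of the low counts, and Section 5.7 lists steroids beside antiemetics and antibiotics. This stands. A reader might infer that a steroid effect is likely to become the primary result, or that the inflation can be put at so many points. The documents support neither inference. They show only that the scoring rule permits the misattribution.

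The plan also has safeguards: low counts confirmed at least twice over 8 weeks before consent, two separated counts for response, and medication review every cycle. The trial is a descriptive pilot with no efficacy threshold, and its intervals are wide (46.3 points at 2/12, from 48.4 − 2.1). These facts lower the stakes. They do not tell a reader which responders were on a newly started steroid.

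A reader might extend the point to androgens, immunomodulatory drugs or erythropoiesis-stimulating agents. The plan does not expressly permit these, and the bar in Section 5.8 on other chemotherapeutic or investigational agents may cover some of them, so the point is confined to corticosteroids. Nor are anemia and symptom response part of the primary result; both are secondary.

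Finally, one might score every patient who starts a steroid before responding as a non-responder, as the sole main analysis. That can discard genuine responses. If 25% of patients started a steroid before responding (an assumption) and the true rate were the 40% used in Section 12.4, up to 0.25 × 0.40 = 10 points would be lost. This objection is sound, and it is why both rates should be reported.

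**Conclusion.** The point holds as a gap in the definition and analysis of response. Section 5.7 permits a co-treatment that the endpoint does not account for, in a trial with no comparator. Each affected responder is worth 8.3 points. The number of such patients, and whether steroids would raise their counts at all, cannot be known from the documents.

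If steroids do not lower platelet counts (an assumption), the rate as defined and the rate without post-steroid counts bracket the proportion of these 12 patients who would have responded without steroids. Reporting both is therefore informative without settling which is right.

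A reader might also infer that Part B eligibility must change. Section 5.3 sets that condition separately, and it governs clinical management. The point concerns how response is reported, not who proceeds or who may receive a steroid. It is a cheap improvement to a descriptive pilot, not a flaw that invalidates it.

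**What to change.** Leave Section 5.7 and the Part B condition in Section 5.3 unchanged.

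1. In Section 12.3, pre-specify that the 12-week platelet response rate is reported with its exact 95% interval in two ways: as defined, and with counts taken after the start or dose increase of a systemic corticosteroid not counted towards response. In the second analysis both qualifying counts must precede that date. Flag each responder whose classification differs.
2. Apply the same pair of analyses to anemia response (Section 10.2.1) and symptom response (Section 10.3), as secondary endpoints.
3. Add to Section 9 a case report form recording corticosteroid start, stop and dose, completed from the medication review already in the Schedule of Activities.

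The cost is one form and one extra analysis per endpoint, with no change to N. The stricter rate will be somewhat low if steroids were given for unrelated reasons; the rate as defined, shown beside it, makes that visible.

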5.8 Prohibited Concurrent Therapy

Patients should not receive treatment with any potent CYP3A4 inhibitors for one week prior to the start of and for the duration of study treatment.

Other chemotherapeutic or investigational agents are not permitted while the patient is receiving active treatment on protocol.

The use of thrombopoietin (TPO) stimulating agents are not permitted while the patient is receiving active treatment on protocol.

Patients cannot receive radiotherapy within 14 days prior to study enrollment or while on study.

5.9 Women of Childbearing Potential

Female subjects must be either post-menopausal for at least 1 year or surgically sterile; or,

if of childbearing potential, must not be pregnant or lactating and must agree to use a highly effective method of birth control throughout the duration of the trial and for 30 days following the last dose. Acceptable methods of birth control are defined as: hormonal contraception (pill, injection or implant) used consistently for at least 30 days prior to screening, an intrauterine device (IUD), or intrauterine hormone-releasing system (IUS), or true abstinence (i.e. abstinence is in line with the preferred and usual lifestyle of the subject.). Male subjects do not need to use contraception for fostamatinib because human studies showed minimal R406 in sperm.

If a patient is suspected to be pregnant, study treatment should be immediately discontinued. In addition, a positive urine test must be confirmed by a serum pregnancy test. If it is confirmed that the patient is not pregnant, the patient may resume dosing.

5.10 Duration of Therapy

If at any time the constraints of this protocol are considered to be detrimental to the patient's health and/or the patient no longer wishes to continue protocol therapy, the protocol therapy should be discontinued and the reason(s) for discontinuation documented in the case report forms.

In the absence of treatment delays due to adverse events, treatment may continue for up to 48 weeks or until one of the following criteria applies:

- Documented and confirmed progression of underlying myelofibrosis
- Death
- Adverse event(s) that, in the judgment of the investigator, may cause severe or permanent harm or which rule out continuation of study drug
- Dose interruptions due to fostamatinib-related AE lasting > 4 weeks (dose interruptions due to other reasons would not warrant permanent discontinuation)
- General or specific changes in the patient's condition render the patient unable to receive further treatment in the judgment of the investigator
- Suspected pregnancy
- Serious noncompliance with the study protocol
- Lost to follow-up
- Patient withdraws consent
- Investigator removes the patient from study
- The Siteman Cancer Center decides to close the study

Patients who prematurely discontinue treatment for any reason will still be followed as indicated in the study calendar.

5.11 Duration of Follow-up

Following the end of treatment, patients will be followed every 6 months for up to 2 years or until the patient is lost to follow up or death, whichever occurs first. Patients removed from study for unacceptable adverse events will be followed until resolution or stabilization

of the adverse event. Decisions regarding future therapy for both responding and refractory patients will be made at the discretion of the treating physician.

5.12 Lost to Follow-Up

A participant will be considered lost to follow-up if he or she fails to return for 3 scheduled visits and is unable to be contacted by the study team.

The following actions must be taken if the participant fails to return to clinic for a required study visit:

- The study team will attempt to contact the participant and reschedule the missed visit within 14 days and counsel the participant on the importance of maintaining the assigned visit schedule and ascertain if the participant wishes to and/or should continue in the study.
- Before a participant is deemed lost to follow-up, the investigator or designee will make every effort to regain contact with the participant (where possible, 3 telephone calls and, if necessary, a certified letter to the participant's last known mailing address). These contact attempts should be documented in the participant's medical record or study file.
- Should the participant continue to be unreachable, he or she will be considered to have withdrawn from the study with a primary reason of lost to follow-up.

6.0 DOSE DELAYS/DOSE MODIFICATIONS

Besides the modifications described below, other dose holds and modifications will be made at the discretion of the PI.

6.1 Dose Modifications for Fostamatinib

For each individual patient, if no AEIs are observed following Cycle 1 of fostamatinib at the starting dose of 100 mg BID, but their platelet count remains $< 50,000/\text{microL}$, then the dose of fostamatinib may be increased to 150 mg BID for all subsequent cycles in the absence of toxicity. Additionally, for each patient whose platelet count improves to $\geq 50,000/\text{microL}$ on 100 mg BID of fostamatinib, but then decreases to $< 50,000/\text{microL}$ after starting ruxolitinib (for at least two platelet measurements at least 2 weeks apart), the dose of fostamatinib may be increased to 150 mg BID for all subsequent cycles.

Dose reductions for fostamatinib will be performed as per the US package insert.

For dose interruptions due to a fostamatinib related AE lasting > 4 weeks, treatment will be permanently discontinued, and the patient will be taken off study.

Recommended Dose Modifications and Management for Specific Adverse Reactions

Adverse Reaction	Recommended Action
Hypertension	
Stage 1: systolic between 130-139 or diastolic between 80-89 mmHg	
 Initiate or increase dosage of antihypertensive medication for patients with increased cardiovascular risk, and adjust as needed until BP is controlled. If the BP target is not met after 8 weeks, reduce fostamatinib to next lower daily dose.
Stage 2: systolic at least 140 or diastolic at least 90 mmHg	
 Initiate or increase dosage of antihypertensive medication, and adjust as needed until BP is controlled. If BP remains 140/90 mmHg or higher for more than 8 weeks, reduce fostamatinib to next lower daily dose. If BP remains 160/100 mmHg or higher for more than 4 weeks despite aggressive antihypertensive therapy, interrupt or discontinue fostamatinib.
Hypertensive crisis: systolic over 180 and/or diastolic over 120 mmHg	
 Interrupt or discontinue fostamatinib. Initiate or increase dosage of antihypertensive medication, and adjust as needed until BP is controlled. If BP returns to less than the target BP, resume fostamatinib at same daily dose. If repeat BP is 160/100 mmHg or higher for more than 4 weeks despite aggressive antihypertensive treatment, discontinue fostamatinib.
Hepatotoxicity	
AST/ALT is 3 x ULN or higher and less than 5 x ULN	
If patient is symptomatic (e.g., nausea, vomiting, abdominal pain):
 
 Interrupt fostamatinib. Recheck LFTs every 72 hours until ALT/AST values are no longer elevated (below 1.5 x ULN) and total BL remains less than 2 x ULN. Resume fostamatinib at next lower daily dose.
	
If patient is asymptomatic:
 
 Recheck LFTs every 72 hours until ALT/AST are below 1.5 x ULN) and total BL remains less than 2 x ULN. Consider interruption or dose reduction of fostamatinib if ALT/AST and TBL remain in this category (AST/ALT is 3 to 5 x ULN; and total BL remains less than 2 x ULN) If interrupted, resume fostamatinib at next lower daily dose) when ALT/AST are no longer elevated (below 1.5 x ULN) and total BL remains less than 2 x ULN.

AST/ALT is 5 x ULN or higher and total BL is less than 2 x ULN	
 Interrupt fostamatinib. Recheck LFTs every 72 hours: If AST and ALT decrease, recheck until ALT and AST are no longer elevated (below 1.5 x ULN) and total BL remains less than 2 x ULN; resume fostamatinib at next lower daily dose. If AST/ALT persist at 5 x ULN or higher for 2 weeks or more, discontinue fostamatinib.
AST/ALT is 3 x ULN or higher and total BL is greater than 2 x ULN	
 Discontinue fostamatinib.
Elevated unconjugated (indirect) BL in absence of other LFT abnormalities	
 Continue fostamatinib with frequent monitoring since isolated increase in unconjugated (indirect) BL may be due to UGT1A1 inhibition
Diarrhea	
Diarrhea	
 Manage diarrhea using supportive measures (e.g., dietary changes, hydration and/or antidiarrheal medication) early after the onset until symptom(s) have resolved. If symptom(s) become severe (Grade 3 or above), temporarily interrupt fostamatinib. If diarrhea improves to mild (Grade 1), resume fostamatinib at the next lower daily dose.
Neutropenia	
Neutropenia	
 If absolute neutrophil count decreases (ANC less than $1.0 \times 10^9/L$) and remains low after 72 hours, temporarily interrupt fostamatinib until resolved (ANC greater than $1.5 \times 10^9/L$). Resume fostamatinib at the next lower daily dose.

ALT = alanine aminotransferase; AST = aspartate aminotransferase; BP = blood pressure; BL = bilirubin; ULN = upper limit of normal; LFT = liver function tests (AST, ALT, total BL with fractionation if elevated, alkaline phosphatase); AST/ALT = AST or ALT

6.2 Dose Modifications for Ruxolitinib

Ruxolitinib dose modifications will be performed as per standard of care. Refer to the package insert for guidance.

7.0 REGULATORY AND REPORTING REQUIREMENTS

The entities providing oversight of safety and compliance with the protocol require reporting as outlined below. Please refer to Appendix D for definitions and Appendix E for a grid of reporting timelines.

Adverse events will be tracked from start of treatment through 30 days after last day of study treatment. All adverse events must be recorded on the toxicity tracking case report form (CRF)

with the exception of:

- Baseline adverse events, which shall be recorded on the medical history CRF

Refer to the data submission schedule in Section 9 for instructions on the collection of AEs in the EDC.

Reporting requirements for Washington University study team may be found in Section 7.1.

7.1 Sponsor-Investigator Reporting Requirements

7.1.1 Reporting to the Human Research Protection Office (HRPO) at Washington University

Reporting will be conducted in accordance with Washington University IRB Policies.

Pre-approval of all protocol exceptions must be obtained prior to implementing the change.

7.1.2 Reporting to the Quality Assurance and Safety Monitoring Committee (QASMC) at Washington University

The Sponsor-Investigator (or designee) is required to notify the QASMC of any unanticipated problems involving risks to participants or others occurring at WU or any BJH or SLCH institution that has been reported to and acknowledged by HRPO. (Unanticipated problems reported to HRPO and withdrawn during the review process need not be reported to QASMC.)

QASMC must be notified within **10 days** of receipt of IRB acknowledgment via email to [contact]. Submission to QASMC must include the myIRB form and any supporting documentation sent with the form.

